**NOTES:**

- \* Case by case basis.
- The list may be updated to reflect any amendments to the PDMP

CONFIDENTIAL

205665

## 14.2. Appendix 2: Schedule of Activities

### 14.2.1. Protocol Defined Schedule of Events

**Table 3 Study Procedures and Assessments**

Procedure 	Screening	Washout	Treatment Period 					Follow-up 	
			Day 1	Day 15	Day 29	Day 43	Day 57	Early WD	Week 10
Informed Consent	X								
Entry Criteria	X								
Physical, Medical History, Demography	X								
HemoCue Hgb	X	X	X 	X	X	X	X 	X	X
Enrolment		X							
IWRS			X	X	X	X			
Randomization			X						
Acute Challenge			X 				X 		
ABPM Assessment			X 				X 		
Dose Adjustment				X	X	X			
Females Only: Serum Pregnancy Test	X		X		X		X		X
Females Only: Estradiol & FSH (if required) 	X								
ECG	X		X 				X 		X
Vital signs & weight (Pre- & Post-dialysis)	X	X	X 		X		X 		X
Clinical Chemistry	X		X		X		X		X
Hematology	X		X		X		X		X
Folate and Vitamin B12	X								
Ferritin, transferrin, total iron, TSAT, UIBC	X								
Pharmacokinetic/Biomarker Assessments			X 				X 		
Hgb Maintenance Period 			←=====→						
Adverse Events Assessment	X 	X	X 	X	X	X	X 		X
Review Concomitant Medications	X	X	X 	X	X	X	X 		X

1 All assessments should be done predialysis/predose except as noted.

2 Allowable time window  $\pm 2$  days EXCEPT Follow-up Visit which is  $\pm 3$  days.

3 As detailed in Inclusion Criteria.

4 Detailed timings for assessments on Acute Challenge Days are given in Table 4.

5 From the end of Acute Challenge 1 to the beginning of Acute Challenge 2.

6 Only SAEs assessed as related to study participation are collected at this visit. See Section 12.4 of the protocol for additional details.

CONFIDENTIAL

205665

**Table 4 Study Procedures and Assessments on Acute Challenge Days (Treatment Period Day 1 and Day 57)**

Procedure	Pre-Dialysis	Post-Dialysis	Predose	Time (in hours relative to dosing)											
				0	0.5	1	2	3	4	6	8	12	16	24	
HemoCue Hgb 			X												X
IWRS			X												
ABPM Assessment 			←----->												
Administer Study Treatment 				X											
Serum Pregnancy Test 			X												
ECG 			X												X
Vital Signs and Weight 	X	X						X					X		X
Clinical Chemistry			X												
Hematology			X												
Pharmacokinetics 			X		X	X	X	X	X	X	X	X	X	X	X
Erythropoietin			X		X	X	X	X	X	X	X	X	X	X	X
Endothelin-1			X			X	X		X	X	X				X
Nitric Oxide			X			X	X		X	X	X				X
Asymmetric dimethylarginine			X			X	X		X	X	X				X
Renin			X			X	X		X	X	X				X
Angiotensin-II			X			X	X		X	X	X				X
Noradrenalin			X			X	X		X	X	X				X
Adverse Events Assessment 			X		X	X	X	X	X	X	X	X	X	X	X
Review Concomitant Medications 			X												X
Initiate Hgb maintenance dosing 															X

1 Procedures to be repeated if Acute Challenge 2 fails quality control criteria

2 Applies to Acute Challenge 1 only

3 Timing of ABPM measurements does not correlate with specified time points in Table 4

4 PK to be drawn from daprodustat participants only

**CONFIDENTIAL**

205665

**14.3. Appendix 3: Assessment Windows****14.3.1. Definitions of Assessment Windows for Analyses**

Data for continuous variables will be summarized according to the scheduled visit time period for which they were recorded in the eCRF. Unscheduled assessments will not be slotted to a particular time point, but will remain as unscheduled if they are either summarized or listed unless otherwise specified.

## 14.4. Appendix 4: Study Phases and Treatment Emergent Adverse Events

### 14.4.1. Study Phases

Assessments and events will be classified according to time of occurrence relative to the treatment start and stop dates.

Treatment States Treatment State	Definition
Pre-Treatment	Date < Treatment Start Date
On-Treatment	Treatment Start Date <= Date ≤ Treatment Stop Date + 1 day
Post-Treatment	Date > Treatment Stop Date + 1 day

**NOTES:**

- If the treatment stop date is missing and the treatment start date is non-missing, then the assessment will be considered to be On-Treatment

#### 14.4.1.1. Study Phases for Concomitant Medication

Pre-treatment medications are those taken (i.e., started) before the start date of randomized treatment. On-treatment medications are those taken (i.e., started or continued) at any time between the randomized treatment start date and the last non-zero dose date + 1 day, inclusive. Pre-treatment medications that were continued during this on-treatment period are also considered to be on-treatment medications. Post-treatment medications are those taken (i.e., started or continued) at any time after the last non-zero dose date + 1 day. On-treatment medications that were continued during this post-treatment period are also considered to be post-treatment medications.

It will be assumed that the medication has been taken on the date in which it is reported as started or stopped. Also, for any medication starting on the same date as randomized treatment, it will be assumed that the medication was taken after the participant started taking randomized treatment.

Illustrations of the pre-treatment, on-treatment, and post-treatment treatment states are included below:

## CONFIDENTIAL

205665

	Pre-treatment	On-treatment			Post-treatment	Pre-treatment medication	On-treatment medication	Post-treatment medication
		Randomized Treatment Start Date	Last Non-zero Dose Date + 1 Day	Last Non-zero Dose Date + 2 Days				
(a)	x—x					Y	N	N
(b)	x—		—x			Y	Y	N
(c)	x—		—	—x		Y	Y	Y
(d)		x—x				N	Y	N
(e)		x—			—x	N	Y	Y
(f)				x—x		N	N	Y
(g)	?—x					Y	N	N
(h)	?—		—x			Y*	Y	N
(i)	?—		—		—x	Y*	Y*	Y
(j)	x—		—		—?	Y	Y**	Y**
(k)		x—			—?	N	Y	Y**
(l)					x—?	N	N	Y
(m)	?—		—		—?	Y***	Y***	Y***
(n)	x—	x				Y	Y	N
(o)	?—	x				Y*	Y	N
(p)		x	—x			N	Y	N
(q)		x	—	x		N	Y	N
(r)				x	—x	N	Y	Y
(s)				x	—?	N	Y	Y**
(t)				x	—x	N	N	Y
(u)				x	—?	N	N	Y
(v)		x—	—	x		N	Y	Y

x = start/stop date of medication

? = missing start/stop date of medication

\* If a medication is stopped On-treatment or Post-treatment and no start date is recorded it will be assumed that the medication was ongoing from the Pre-treatment phase

\*\* If a medication is started Pre-treatment or On-treatment and no stop date is recorded then usage will be assumed to be ongoing for the remainder of the study

\*\*\* If a medication has no start or stop date it will be assumed that the medication was ongoing from the Pre-treatment phase to the Post-treatment phase

## CONFIDENTIAL

205665

**14.4.2. Treatment Emergent Flag for Adverse Events**

All AEs (non-serious AEs and serious AEs) will be collected and recorded on the eCRF from the start of treatment, including washout period, until the follow-up visit at the time points specified in the SoA from [Appendix 2](#). Serious AEs assessed as related to study participation (e.g., study treatment, protocol-mandated procedures, invasive tests, or change in existing therapy) or related to a GSK product will be recorded on the eCRF from the time a participant consents to participate in the study up to and including any follow-up contact.

Treatment State	Definition
Pre-treatment	
 
For participants with a non-missing screen failure date, if AE onset is on or before the screen failure date: AE Start Date <math>\leq</math> Screen Failure Date
 
For randomized participants with a missing treatment start date, all AEs are considered pre-treatment
 
For randomized subjects with a non-missing treatment start date, if AE onset date is before treatment start date: AE Start Date <math><</math> Treatment Start Date
 

Post-randomization	If AE onset date or AE worsening date is on or after the randomization date Randomization date $\leq$ AE Start Date Randomization date $\leq$ AE Worsening Date
Treatment emergent	If AE onset date or AE worsening date is on or after treatment start date & on or before the last non-zero dose date plus 1 day. Treatment Start Date $\leq$ AE Start Date $\leq$ Last Non-Zero Dose Date + 1 day Treatment Start Date $\leq$ AE Worsening Date $\leq$ Last Non-Zero Dose Date + 1 day
Follow-up	If AE onset date or AE worsening date is after the last non-zero dose date plus 1 day. AE Start Date $>$ Last Non-Zero Dose Date + 1 day AE Worsening Date $>$ Last Non-Zero Dose Date + 1 day
Onset /Worsening Time Since 1 st Dose (Days)	If Treatment Start Date $>$ AE Onset Date = AE Onset Date - Treatment Start Date + 1 If Treatment Start Date $\leq$ AE Onset Date = AE Onset Date - Treatment Start Date + 1 If Treatment Start Date $>$ AE Worsening Date = AE Worsening Date - Treatment Start Date If Treatment Start Date $\leq$ AE Worsening Date = AE Worsening Date - Treatment Start Date + 1 Missing otherwise.
Onset/Worsening Time Since Last Dose (Days)	If Last Non-Zero Dose Date $<$ AE onset date: AE onset date – last non-zero dose date If Last Non-Zero Dose Date $\geq$ AE onset date: AE onset date – last non-zero dose date If Last Non-Zero Dose Date $<$ AE worsening date: AE worsening date – last non-zero dose date If Last Non-Zero Dose Date $\geq$ AE worsening date: AE worsening date – last non-zero dose date Missing otherwise.
Duration (Days)	AE Resolution Date – AE Onset Date/AE Worsening Date + 1
Drug-related	If relationship is marked 'YES' on eCRF or if the value is missing.

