4. STUDY DESIGN

4.1. Overall Design

This study will be an open-label, randomized, parallel-group design in HD subjects with anemia associated with CKD. There will be a screening period, a 2-week ESA washout

period, an initial 24-hr Acute Challenge, an 8-week Hgb-maintenance period, a second 24-hr Acute Challenge and a follow-up visit 14±3 days after completing treatment. The study design is outlined in [Figure 1](#).

Figure 1 Study Design

Subjects will be screened for eligibility within 7-30 days prior to the start of an ESA washout period.

Subjects that qualify for enrolment will be washed out of their ESA for 2 weeks; the start of the ESA washout should be timed to coincide as closely as possible with their next planned ESA dose. Subjects are enrolled once they enter the ESA washout period.

Following the 2-week ESA washout, subjects will be randomized 1:1 and stratified by prior ESA dose, based on the average weekly (for epoetins or darbepoetin) or monthly (for methoxy polyethylene glycol (PEG)-epoetin beta) dosing during the 12 weeks prior to ESA washout as follows:

- Low ESA dose: <100 U/kg/week epoetin alfa OR <0.5 µg/kg/week darbepoetin OR <0.6 µg/kg/week methoxy PEG-epoetin beta
- High ESA dose: ≥100 U/kg/week epoetin alfa OR ≥0.5 µg/kg/week darbepoetin OR ≥0.6 µg/kg/week methoxy PEG-epoetin beta

On Day 1, subjects will be randomized and undergo Acute Challenge 1, a single dose challenge to compare the acute effects on BP of the highest planned once-daily maintenance dose of daprodustat (24 mg) to the highest starting dose of epoetin alfa (100 U/kg). Subjects will have BP monitored for 24 hr using ABPM, and will have serial blood sampling to assess the pharmacokinetics of daprodustat and the time-course of various biomarkers. Acute Challenge 1 will be started promptly following completion of a mid-week dialysis session.

After completing Acute Challenge 1, all subjects will enter the 8-week Hgb maintenance period where doses of either daprodustat or epoetin alfa will be administered and adjusted, as needed, based on dosing guidance as described in [Section 6.4](#).

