7.3.1.1. Time Period and Frequency for Collecting AE and SAE Information

- Any SAEs assessed as related to study participation (e.g., protocol-mandated procedures, invasive tests, or change in existing therapy) or related to a GSK product will be recorded from the time a subject consents to participate in the study up to and including any follow-up contact.
- AEs will be collected from the start of washout until the follow-up contact (see Section 7.3.1.3), at the timepoints specified in the Time and Events Table (Section 7.1).
- Medical occurrences that begin prior to the start of washout but after obtaining informed consent may be recorded on the Medical History/Current Medical Conditions section of the CRF.
- All SAEs will be recorded and reported to GSK within 24 hours, as indicated in Section 12.4. The investigator will submit any updated SAE data to the sponsor within 24 hours of it being available.
- Investigators are not obligated to actively seek AEs or SAEs in former study subjects. However, if the investigator learns of any SAE, including a death, at any time after a subject has been discharged from the study, and he/she considers the event reasonably related to the study treatment or study participation, the investigator must promptly notify GSK.

NOTE: The method of recording, evaluating and assessing causality of AEs and SAEs plus procedures for completing and transmitting SAE reports to GSK are provided in Section 12.4.

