**CONFIDENTIAL**

205665

A listing of which participants reported specific adverse events will be produced.

The hierarchical relationship between MedDRA SOCs, PTs and verbatim text will be listed for all adverse events.

Adverse events occurring during the 24-hour acute challenge will be grouped in the appropriate acute challenge phase. Any AE occurring after AC2 but before repeat-AC2 will be grouped in the HGB maintenance phase.

Adverse events occurring after the last on treatment date will be grouped either in early withdrawal or follow-up depending on the final status of the subject,

*Serious and Other Significant Adverse Events*

The number and percentage of participants and the number of occurrences of SAEs will be provided for each treatment group. These events will be summarized by treatment group, primary system organ class, and preferred term. Pre-treatment, post-randomization, treatment emergent and follow-up SAEs will be summarized separately. Treatment emergent SAE preferred terms will also be summarized by treatment group and overall frequency.

A listing of reasons for considering as a SAE will be produced for all treatment emergent SAEs.

The number and percentage of participants and the number of occurrences of treatment emergent drug-related SAEs, and drug-related fatal SAEs will be summarized by treatment group.

A listing of treatment emergent fatal SAE records and a listing of treatment emergent non-fatal SAE records will be provided.

The number and percentage of participants reporting treatment emergent AEs leading to discontinuation of randomized treatment will be summarized by treatment group, primary system organ class, and preferred term.

A listing of treatment emergent AEs leading to discontinuation of randomized treatment will be provided.

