## **8.2. Adverse Events of Special Interest Analyses**

A comprehensive list of MedDRA terms based on clinical review will be used to identify each type of event. [Changes to the MedDRA dictionary may occur between the start of the study and the time of reporting and/or emerging data from on-going studies may highlight additional adverse events of special interest, therefore the list of terms to be used for each event of interest and the specific events of interest will be based on the safety review team (SRT) agreements in place at the time of reporting.] The details of the planned displays are provided in [Appendix 12: List of Data Displays](#). See Section [14.6.4](#) for complete list of AESIs

Summaries of AESIs will include the number, percentage and rate per 100 person-years of participants having at least one occurrence, the number of events, the number of participants by number of occurrence, the characteristics of the AE (serious, drug-related, etc.), outcome, maximum intensity, time to first onset/worsening, the duration of first, second, and third occurrence of the AE, and action taken summarized by treatment group. For each count, a participant will be summarized as follows:

- Serious/drug-related/severe/fatal: If any specific AE falls in the respective category, the participant will be counted in that category.
- Outcome: The participant will be counted within a category if there is at least one specific AE in that category.
- Maximum intensity: The specific AE with the maximum intensity will be counted for this purpose. For example, a participant will be counted in the ‘severe’ category if there is at least one specific AE with severe intensity. A participant will be counted in the ‘moderate’ category if there is at least one specific AE with moderate intensity and there is no specific AE with severe intensity.
- Time to first onset/worsening (days): The earliest of onset dates for the specific AE – treatment start + 1
- Duration of the occurrence (days): AE resolution date – AE onset date/AE worsening date + 1 for the occurrence

If the AE onset date/AE worsening and/or resolution date is missing or incomplete in the database for any occurrence of the specific AE, time to first onset/worsening and/or duration of the first, second, and third occurrence will be left missing for the participant. These summaries of special interest AEs will be provided for those AEs classified as treatment emergent, follow-up and post-randomization.

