#### **General Definitions**

- For the analysis of the time to AE onset/worsening, if the AE onset/worsening date is missing then the time to AE onset/worsening will be counted as 1 day.

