#### 14.7.2.1. Handling of Missing and Partial Dates

Element	Reporting Detail
General	
 
Partial dates will be displayed as captured in participant listing displays.
 

Adverse Events	
 
The eCRF allows for the possibility of partial dates (i.e., only month and year) to be recorded for AE start and end dates; that is, the day of the month may be missing. In such a case, the following conventions will be applied for calculating the time to onset and the duration of the event: 
 
Missing Start Day: First of the month will be used unless this is before the start date of study treatment; in this case the study treatment start date will be used and hence the event is considered On-treatment as per Appendix 4: Study Phases and Treatment Emergent Adverse Events.
 
Missing Stop Day: Last day of the month will be used, unless this is after the stop date of study treatment; in this case the study treatment stop date will be used.
 
 
 
Completely missing start or end dates will remain missing, with no imputation applied. Consequently, time to onset and duration of such events will be missing.
 

Concomitant Medications/ Medical History	
 
Partial dates for any concomitant medications recorded in the CRF will be imputed using the following convention: 
 
If the partial date is a start date, a '01' will be used for the day and 'Jan' will be used for the month
 
 
 

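### SAP 14.6.4 counts a missing AE onset date as onset on Day 1, while three other SAP rules leave time to onset missing

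*SAP*

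**What the plan says.** Four places in the SAP give a time to onset for an AE with no onset date.

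- The general definitions in 14.6.4 say that "if the AE onset/worsening date is missing then the time to AE onset/worsening will be counted as 1 day". The sentence covers the analysis of time to onset or worsening and names no particular output.
- Section 8.2, for AESIs, defines time to first onset as the earliest onset date minus treatment start, plus 1. If a date is missing or incomplete for any occurrence, "time to first onset/worsening and/or duration of the first, second, and third occurrence will be left missing for the participant".
- Section 14.7.2.1 imputes nothing when a start date is completely missing: "Consequently, time to onset and duration of such events will be missing". If only the day is missing it does impute, using the first of the month, or the treatment start date if that is later.
- Section 14.4.2 derives onset time since first dose from the dates and sets it to missing when they do not allow it.

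The notes to 14.4.2 classify an undated AE as treatment-emergent unless its resolution date is before treatment start.

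The flag itself uses calendar dates. An AE is pre-treatment under the condition "For randomized subjects with a non-missing treatment start date, if AE onset date is before treatment start date" and treatment-emergent under the condition "If AE onset date or AE worsening date is on or after treatment start date". The protocol (4.1) puts dialysis before the first dose on the same day: "Acute Challenge 1 will be started promptly following completion of a mid-week dialysis session". AE collection has begun by then: "AEs will be collected from the start of washout until the follow-up contact" (protocol 7.3.1.1). For the table of AEs by phase (Table 2.2), SAP 8.1 says: "Adverse events occurring during the 24-hour acute challenge will be grouped in the appropriate acute challenge phase".

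**The concern.** A programmer who follows 14.6.4 and one who follows 8.2 will produce different time-to-onset results from the same data. The 14.6.4 value is not neutral. It gives an event of unknown timing an onset on Day 1, the day on which participants receive the 24 mg daprodustat or 100 U/kg epoetin alfa challenge dose. Worsening of hypertension is one of the AESIs, so an invented Day 1 onset is an unhelpful default in a study of acute blood pressure effects.

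The date-only flag raises a smaller question about the same day. It cannot separate an event during the pre-dose dialysis from one after the dose.

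**Working it through.** **1. What 1 day means.** Section 8.2 gives time to onset = onset date − treatment start date + 1. Setting this to 1 gives onset date = treatment start date. The value in 14.6.4 is therefore a Day 1 onset.

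**2. The rules side by side.** Partial dates are illustrated with treatment start on 8 January 2020.

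| Rule | Date fully missing | January, day unknown | February, day unknown |
|---|---|---|---|
| 14.6.4 | 1 day | not addressed | not addressed |
| 8.2 | missing | missing | missing |
| 14.7.2.1 | missing | 1 January is before treatment start, so 8 January is used: 8 − 8 + 1 = 1 day | 1 February: 24 + 1 = 25 days |
| 14.4.2 | missing | not addressed | not addressed |

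On fully missing dates, 14.6.4 stands against the other three. On partial dates there is a second conflict: 8.2 leaves the time missing and 14.7.2.1 supplies a date.

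**3. Whether it reaches an output.** Under the notes to 14.4.2 an undated AE is treatment-emergent if its resolution date is missing or is on or after treatment start. Section 8.2 summarizes AESI time to onset for treatment-emergent events, so the conflict applies there.

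**4. Illustration of effect (made-up data).** Take four participants with an AESI, three with onset on days 20, 35 and 50 and one undated. If the undated time is left missing, the median is 35. If it is set to 1, the ordered values are 1, 20, 35 and 50, and the median is (20 + 35)/2 = 27.5.

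**5. The date-only flag.** Three test events, classified by date as in 14.4.2 and by clock time against the dose:

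| Event | By date | By time |
|---|---|---|
| Day before first dose | not treatment-emergent | not treatment-emergent |
| Day 1, 2 h before dose | treatment-emergent, onset day 1 | not treatment-emergent |
| Day 1, 1 h after dose | treatment-emergent, onset day 1 | treatment-emergent |

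Only the pre-dose event changes. One participant is 1/31 = 3.23% of an arm of 31, or 1/25 = 4.00% of 25. Both exceed the 2% threshold for the common-AE tables, so one such event is enough to list a preferred term. That is true of any single event, in either arm.

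**The case against.** On undated events, the best defence is that exposure is small. Section 14.7.2.1 describes partial AE dates as lacking only the day, so completely missing dates may be rare. The Kaplan-Meier plots in 8.2 are optional, the display numbering in 14.12.1 reserves no safety figures, and the one listed AESI table (2.11) uses a general AE shell. The 14.6.4 sentence may have been written for those plots alone. This limits the size of the problem but does not remove it. The sentence does not restrict itself to plots, and 8.2 describes a time-to-onset summary whatever happens to the plots. The sentence sets a time value only. It assigns no onset date or phase and cannot add events to Table 2.2.

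On the date-only flag, a reader might infer that intradialytic events will contaminate the acute-challenge phase and be blamed on the challenge dose. The documents do not support that:

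- Counting same-day events as on-treatment is a conservative convention, consistent with the treatment states in 14.4.1 and the medication rule in 14.4.1.1.
- Dialysis precedes the dose in both arms, so the effect should be similar in each.
- Treatment-emergent is a timing flag. Drug-relatedness is the investigator's judgement and is tabulated separately.
- Section 8.1 groups by the 24-hour challenge, which begins after dialysis.

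Some ambiguity remains. SAP 5.1 labels Acute Challenge 1 as Day 1 and the maintenance phase as Days 2 to 56. An event 20 hours after the dose, usually on Day 2, is therefore in the challenge under 8.1 and in maintenance under 5.1.

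A reader might also put a number on it. A 5 to 10% AE rate per dialysis session would give 62 × 0.05 = 3.1 to 62 × 0.10 = 6.2 participants. The documents give no such rate, and protocol 12.4.1 excludes some expected symptoms from the AE definition, so no count can be stated.

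**Conclusion.** The conflict on undated events is real and should be corrected. Section 14.6.4 assigns Day 1 where 8.2, 14.7.2.1 and 14.4.2 assign nothing, and the Day 1 value has no basis in data. A related conflict on partial dates lies between 8.2 and 14.7.2.1. The consequence is confined to AE time-to-onset outputs, mainly those for AESIs. Its size depends on how many AEs lack an onset date, which the documents do not give. Undated events should not be described as events that began before the dose, because their onset is simply unknown.

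The calendar-date flag is a limitation to disclose, not an error. It makes an event that starts during the Day 1 dialysis treatment-emergent in both arms. Protocol Table 4 schedules AE assessments before the dose and at set times after it, but neither document shows that onset time or assessment slot is recorded with the AE.

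**What to change.** 1. Delete the sentence in 14.6.4, so that a completely missing onset date gives a missing time to onset everywhere.
2. In 8.2, confine the leave-missing rule to completely missing dates, and use the dates imputed under 14.7.2.1 for partial ones. A partial date in the month of first dose may then fall on Day 1, so footnote the imputation. If Kaplan-Meier plots are produced, state how many undated events have no place on the curve.
3. If AE onset time or the pre/post-dose assessment slot was captured, apply the 24-hour grouping of 8.1 in Table 2.2 by time relative to the dose on Days 1 and 57. Events of unknown time, and any event that worsens after the dose, stay treatment-emergent. If timing was not captured, footnote the same-day convention.

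Items 1 and 2 cost a deleted sentence and a small change of wording. Item 3 costs one derivation if the timing data exist, and a footnote if they do not.
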